8.4 Investigational Products

8.4.1 Investigational Products Administered

ND0612, a LD/CD solution, with a LD concentration of 60 mg/mL and CD concentration of 7.5 mg/mL will be administered in this clinical study using an infusion pump system, CRONO Twin ND, for daily doses up to 720 mg LD/ 90 mg CD (12 mL).

Three dosing regimens of ND0612 will be studied in this study as described in Section 8.1.1 (see also dosing table in Section 8.4.7).

The ND0612 infusion pump system is comprised of a pump CRONO TWIN ND, manufactured by CANE for ambulatory use, two 10 mL syringes, and two infusion sets, which are commercially available or approved for use and are assembled from a tube and a cannula. Additional ancillary supplies may be provided as needed.

The study site staff will program the infusion rates and time of administration data in the pumps, and will be trained for reprograming infusion rates for up and down titration purposes.

The cannulas should be inserted into the SC layer. The recommended infusion sites are in the abdomen (including flanks) and outer thighs. It is recommended to insert the cannula with the assistance of an insertion device. During the treatment initiation, this will be supervised by the study site staff. During the treatment period subjects/study partners will handle the administration of the infusion and the operation of the pump system after having been provided with appropriate training. Refer to Section 8.1.1.1 for instructions regarding management of the infusion sites.

Treatment with ND0612 will be initiated in the following steps:

- 1. Program the pump to deliver the infusion rates according to the assigned treatment regimen
- Initiate ND0612 while continuing adjunct oral LD/DDI, and gradually down titrating the oral LD dose. For subjects with a low baseline total dose of LD (≤ 700 mg per day), consider significantly reducing or stopping the oral LD/DDI that is taken as adjunct therapy upon initiation of ND0612 (please note the morning dose of Regimen 3 must be given). The ND0612 dose may also be down titrated (refer to Section 8.4.9.3 for further instructions).
- 3. For troublesome dyskinesia, or other troublesome levodopa related adverse reactions consider first reducing the dose of oral LD/DDI that is taken as adjunct therapy. If complications persist, the hourly high day rate of the ND0612 infusion may be down titrated.
- 4. Titrate the dose of adjunct oral LD/DDI, and the ND0612 dose based on the subject's individual clinical response and tolerability until a stable daily regimen is maintained.
- 5. Extra doses of oral LD/DDI can be used to manage "OFF" symptoms that are not controlled by the continuous ND0612 infusion

ND0612 dose may be decreased if required per the Investigator's decision. In the event a subject experiences dopaminergic complications, oral LD/DDI taken as additional therapy (if any) should be reduced/stopped first. If complications persist, the hourly high infusion rate may be down titrated. Every 0.05 ml/h increment is equivalent to \sim 50 mg LD reduction per day. There is no cap to the number of dose reductions a subject may require. Subjects tolerating a dose reduction for 72 hours may attempt to up-titrate again. Subjects must come to the clinic for any up or down titrations as the pump must be reprogrammed to accommodate the new flow rate.

Abrupt discontinuation or significant dose reductions of the study treatment should be avoided. The study drug dosing should be gradually reduced.

In case of any problem in the pump system that cannot be fixed within 3 hours, the subjects should contact the Investigator and the helpline, and resume a regimen of oral LD/DDI until the study drug administration can be continued.

Study drug and clinical supplies for 1 month will be dispensed on the clinic visits at Baseline and Months 1, 2, 3, 4, 6, 9. On months 5, 7, 8, 10, 11, study drug and clinical supplies for 1 month will be dispensed to the subject, or the study partner at a clinic visit dedicated to study medication dispensing, Alternative means of medication distribution (e.g., via courier) may be used following regulatory and EC approval.

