8.4.9.3 Down Titration of Study Drug During the Treatment Period of the Study

ND0612 dose may be decreased if required per the Investigator's decision. In the event a subject experiences dopaminergic complications in the opinion of the clinical investigator, oral LD/DDI or entacapone taken as additional therapy (if any) should be reduced/stopped first. If complications persist, the hourly high infusion rate may be down titrated. Every 0.05 mL/hr increment of ND0612 infusion rate is equivalent to ~50 mg LD reduction per day. There is no limitation to the number of dose reductions a subject may require. Subjects not tolerating a dose reduction may attempt to up-titrate again. Both down and up titrations of study drug and additional therapy are at the discretion of the investigator. The morning dose of oral LD/CD IR in Regimen 3 is not to be reduced. Subjects must come to the clinic for any up or down titrations of the study drug as the pump must be reprogrammed to accommodate the new flow rate.

Subjects with a low total dose of LD at baseline (\leq 700 mg per day) should receive special consideration. In such cases, upon initiation of SC infusion on Day 1, oral LD/DDI may be significantly reduced or stopped (please note the morning dose of Regimen 3 must be taken); the ND0612 hourly high infusion rate may be down titrated as well.

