11.2 Determination of Sample Size

A sample size of approximately 210 treated subjects was considered appropriate for evaluating the long-term safety and tolerability of ND0612 administered at the 2 study regimens, Regimen 1 and Regimen 3, with a focus on local tolerability at the infusion sites. No formal sample size evaluation has been conducted. Since the maximum size of Cohort 1 is limited (36 subjects were to be treated in study ND0612H-006) the majority of subjects will be included in Cohort 2.

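### Protocol 8.4.1 and 8.4.9.3 state reversed conditions for raising ND0612 again after a dose reduction, and only one gives a 72-hour period

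*Protocol*

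**What the plan says.** Two sections of the current protocol body (Version 10.0) describe what may happen after the ND0612 infusion rate has been lowered.

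- Protocol 8.4.1 (Investigational Products Administered): "Subjects tolerating a dose reduction for 72 hours may attempt to up-titrate again".
- Protocol 8.4.9.3 (Down Titration of Study Drug During the Treatment Period of the Study): "Subjects not tolerating a dose reduction may attempt to up-titrate again". The next sentence there reads: "Both down and up titrations of study drug and additional therapy are at the discretion of the investigator".

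Section 8.4.1 links the two in its initiation steps: "The ND0612 dose may also be down titrated (refer to Section 8.4.9.3 for further instructions".

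Protocol 6.5 says the study will explore the need for dose adjustments, both up and down. Protocol 11.1.4.3.1 lists two exploratory endpoints on the ND0612 dose: the change in total dose from baseline to Month 12, and the proportion of patients who reduced the total dose at any time. SAP 3.2.3.5, 3.2.3.6 and 3.2.3.16 carry these over. SAP 7.2 adds the number of patients who reduced dose and the mean reduction from baseline to each visit.

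**The concern.** The same action, raising the dose again, is tied in one section to tolerating the reduction and in the other to not tolerating it. One section attaches a period of 72 hours and the other attaches none. This is an operative dosing instruction, not background text. Investigators at about 65 planned sites (Protocol 8.3.1) could follow either section and be in line with the protocol.

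Two things are at stake. The first is subject safety. In both sections the paragraph deals with reductions that may be made for dopaminergic complications, so the criterion and timing for going back up matter to the subject. The second is the dose data. When and for whom a reduced dose is raised again feeds into the dose recorded at later visits, so differences in site practice could be mixed with differences in patient need.

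**Working it through.** The point concerns wording. No planned figure is involved, and Protocol 11.2 states of the sample size: "No formal sample size evaluation has been conducted". The check is a side-by-side reading, followed by a test of whether the numerical step also differs.

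**1. Do the two paragraphs govern the same situation?**

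| Element | Protocol 8.4.1 | Protocol 8.4.9.3 |
|---|---|---|
| Who decides on a reduction | Investigator | Investigator |
| What is reduced first | Additional oral LD/DDI | Additional oral LD/DDI or entacapone |
| Next step if complications persist | Lower the hourly high rate | Lower the hourly high rate |
| Size of step | 0.05 mL/h, about 50 mg LD per day | Same |
| Number of reductions | "There is no cap to the number of dose reductions a subject may require" | "There is no limitation to the number of dose reductions a subject may require" |
| Condition for going up again | Tolerating the reduction | Not tolerating the reduction |
| Waiting period | 72 hours | None stated |
| Where the change is made | Clinic visit to reprogram the pump | Same |

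Section 8.4.9.3 adds entacapone, the discretion sentence and a statement on the Regimen 3 morning oral dose. It names no different population or study period that would explain a different trigger. These are two statements of one rule, and they part only at the up-titration condition and its timing.

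**2. Is the step size consistent?** Section 8.4.9.3 introduces it with the words "increment of ND0612 infusion rate is equivalent to", followed by about 50 mg LD per day. The formula is step (mL/h) × hours at the high rate × LD concentration (mg/mL). The concentration is 60 mg/mL (Protocol 8.4.2) and the hours are from Protocol Table 2.

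- Regimen 1: 0.05 × 18 × 60 = 54 mg LD per day.
- Regimen 3: 0.05 × 16 × 60 = 48 mg LD per day.

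Both agree with the rounded figure in the protocol. The inconsistency does not extend to the step size.

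**3. Does anything else resolve it?** Protocol 8.4.7 and 9.2.9 send the reader to 8.4.9.2 for dose and pump-rate adjustment. That section covers rescue and additional anti-PD therapy and gives no condition for raising ND0612 again. The SAP gives none either.

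**4. Which outputs could move?**

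- *Change in ND0612 total dose to Month 12, and mean reduction by visit.* Both depend on whether a reduction is still in place at the visit. For one subject on the full regimen, a single step reversed or left in place changes the recorded dose by 48 or 54 mg per day. Against 720 mg that is 48/720 = 6.7% or 54/720 = 7.5%.
- *Proportion who ever reduced dose.* A later increase does not undo an earlier reduction, so this should be little affected.

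**5. Can the overall effect be sized?** No. The documents give neither the expected number of subjects with a reduction nor how often an increase would then be considered.

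**The case against.** The strongest reply is that the two sentences do not conflict in law or in practice. Both are permissive: neither forbids what the other allows, and neither compels an increase. Section 8.4.9.3 leaves all titration to the investigator, and step 4 of the initiation list in 8.4.1 already ties titration to individual response and tolerability. Every rate change needs a clinic visit, the daily dose is limited to 720/90 mg LD/CD, and unscheduled visits record adverse events and concomitant medication at a minimum (Protocol 9.2.9). The affected dose endpoint is exploratory.

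Much of this stands, and it limits the point. A reader might infer that sites have been given mutually exclusive orders, or that they will diverge. The documents support neither: the wording is permissive, discretion is explicit, and nothing shows that practice differed. A reader might also infer that every subject with a reduction is affected. The sentences matter only when an increase is being considered.

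The reply does not remove the inconsistency. If both sentences are read together, subjects who tolerate the reduction may go up after 72 hours and those who do not tolerate it may go up at any time. Tolerance would then decide only the timing. Neither section states that combined rule, and a site reading one section would not arrive at it. Discretion does not tell the investigator which written criterion to start from.

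**Conclusion.** The point holds as an internal inconsistency that is wrong as written; it is not a criticism of a design choice. The written criterion for raising ND0612 after a reduction is reversed between Protocol 8.4.1 and 8.4.9.3, and the 72-hour period appears only in 8.4.1. Sites could therefore apply different criteria and timing.

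The possible consequences are for subject safety, for the exploratory change in ND0612 total dose to Month 12, and for the mean reduction by visit in SAP 7.2. On safety, the documents establish a possibility only; they give no rate or size of harm. It is tempting to extend the point to all dose-reduction endpoints, but the proportion who ever reduced dose is fixed by the first reduction. It is also tempting to treat one of the two sentences as a simple misprint. The documents do not show which version was intended.

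The conclusion assumes that the two paragraphs are meant as one rule, which their parallel content and the cross-reference support. The per-subject figures assume one step from the full regimen at the hours in Table 2.

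**What to change.** The sponsor must reconcile Protocol 8.4.1 and 8.4.9.3 into a single statement of the condition and timing for raising ND0612 after a reduction, and use it in both sections, or state it once and cross-refer. If two separate situations were meant, both should be set out together, with the timing that applies to each. Which condition and which period apply is for the sponsor to settle; none is proposed here.

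The cost is a protocol text clarification and notice to the sites. The design, the analysis sets and the planned analyses do not change.

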8.4.2 Identity of Investigational Products

Characteristics of test product:

Substance: Levodopa/carbidopa

Pharmaceutical form: solution for infusion supplied in a glass vial closed with a rubber stopper.

```
Manufacturer: CATALENT Indiana LLC
[name]
```

Unit Strength: LD 60 mg/mL / CD 7.5 mg/mL

Route of administration: SC infusion (rates and duration of infusion depending on regimen)

The study drug ND0612 will be manufactured and imported according to the applicable regulatory requirements.

The study drug ND0612 will be infused using a pump system; CRONO TWIN ND pump system, manufactured by CANE. The pump system is comprised of a pump, two special syringes and two infusion sets with an insertion device.

8.4.3 Study Drug Packaging and Labeling

The secondary packaging and labeling of study drug will be performed by PCI -Packaging Coordinators Inc. (Rockford office: [name]).

All packaging and labeling operations for study drug will be performed according to Good Manufacturing Practice for Medicinal Products and the relevant regulatory requirements.

Distribution and Shipment:

ND0612 will be shipped frozen to the study site (or Central Pharmacy, where applicable), under the sponsor's responsibility. All study drugs will be packed in

appropriate storage boxes. If, upon arrival at the investigational site, the study drugs appear to be damaged, the sponsor or designee should be contacted immediately. Each shipment of study drug for the study will contain a shipment form describing the content of shipment. This form will assist in maintaining current and accurate inventory records. When a shipment is received, the investigator or designee will acknowledge receipt of the study drugs by signing the relevant shipping documents and recording arrival of the shipment in the Interactive Web Response System (IWRS).

Storage Conditions for ND0612

ND0612 will be kept at the site in a freezer at -20° C \pm 5 °C in a secure, limited-access, controlled storage area.

Only authorized personnel will have access to the study drugs. The study site personnel at each site or Central Pharmacy will be responsible for correct storage and handling of the study drugs.

Study drug is packed in drug kits. Each kit will contain 72 drug vials. Each drug kit will be labelled with the protocol number, storage information, warning language (i.e., as required by local legislation for investigational drug products), dosing and storage instructions. The kit should be taken out of the freezer at least 4 hours before dispensing and kept at room temperature. Before dispensing or shipping of study drug kits, the dispensing study staff member or Central Pharmacy staff will write on the label the Subject's Study ID number and the last date to use after thawing.

Once study drug is dispensed or shipped to a subject, it may be shipped at ambient temperatures from the site or Central Pharmacy to the subject's home and stored at home at room temperature $(15^{\circ}C-30^{\circ}C, 59^{\circ}F-86^{\circ}F)$, out of the reach of children. The study drug should NOT be placed in the refrigerator. Storage at room temperature must not exceed 35 days from thawing day. Before use, the vials should be tilted gently to verify that the content is uniform and is a clear slightly yellowish to yellowish solution without visible particles.

8.4.4 Direct-to-Patient (Supplies) Model

In case a study site is unavailable to receive IP shipments and/or dispense IP to subjects, a Central Pharmacy may be used (where regulatory applicable) to perform these activities directly to subject's home. A designated courier approved by the Sponsor will ship the required supplies. When this option will be applicable, specific procedures of working with a Central Pharmacy will be specified in a specific clinical supplies manual for the Central Pharmacy.

8.4.5 Method of Assigning Subjects to Treatment Groups

The original plan in this study was that subjects in Cohort 1 remain on the regimen they received in study ND0612H-006; subjects in Cohort 2 were to be randomized to one of the two treatment regimens (Regimen 1 or 2) at a ratio of 1:1. Following the recommendation of the ND0612H-006 oversight committee, the sponsor decided to discontinue Regimen 2 treatment on 08 December 2016. At that point 12 subjects were included in Regimen 2, and all but 2 subjects (who had already been discontinued at that time) on Regimen 2 were transitioned to Regimen 1. The sponsor decided to further evaluate an optimized daily treatment regimen (Regimen 3) of 16 hr at a rate of 0.75 mL/hr; after Protocol amendment 2, all newly enrolled subjects in Cohort 2 were to receive Regimen 3.

Each subject will receive a unique subject number when study staff enter them into the IWRS after they have provided informed consent. Subjects will retain their assigned subject number for the duration of the study; the subject numbers consist of a 3-digit site number and a 3-digit sequential number (i.e., xxx-xxx). Every subject must provide informed consent before any study procedures are conducted. Every subject that provides informed consent must be entered into the IWRS system regardless of eligibility. All subjects who are consented will also have their data entered into the electronic data capture (EDC) system. Subjects who are screen failures will only need to have limited data entered, including the reason for failing screening.

Subjects will enter the treatment period after all screening procedures (if applicable) and baseline assessments have been performed and eligibility for the study has been confirmed. Enrolled subjects who terminate their study participation for any reason, regardless of whether any study medication was received or not, will retain their screening number and randomization number (if applicable) and the study staff will need to enter the information into the IWRS to discontinue the subject's participation in the study.

Randomization was performed in Cohort 2 before implementation of Protocol amendment 2 as follows. In order to ensure a balanced treatment allocation, subjects in Cohort 2 were to be randomized in a 1:1 ratio to receive either Regimen 1 or Regimen 2. A stratification by region was performed. IWRS assigned a unique randomization ID for each randomized subject and assigned subjects to a treatment regimen based on the pre-defined randomization schedule. Syneos Health biostatistics prepared the master randomization schedule, which was imported into the IWRS using a validated program.

Subjects who are withdrawn from the study and/or study treatment will not be replaced.

The Sponsor reserves the right to switch all subjects to one of the above 2 regimens, based on the results of the ND0612H-006 study. In this case, ongoing subjects will be switched at their next scheduled study visit and subjects not yet randomized will be allocated to the selected regimen instead of being randomized. Such a decision was taken on 08 December 2016, when Regimen 2 was discontinued.

8.4.6 Selection of Doses in the Study

A rationale for the selection of doses in this study is provided in Section 8.2.

8.4.7 Selection and Timing of Dose for Each Subject

The daily dosing in the study regimens is summarized in Table 2 (below). Dose adjustments can be made as described in Section 8.4.9.2.

Treatment	Formulation LD/CD	No. of Infusion Sites	Infusion Rate	Total Volume (mL/24h)	Total LD Dose (mg/24h)	Total CD Dose (mg/24h)	Timing	Oral LD/DDI	Wear Pump Over-night
Regimen 1			0.08 mL/hr for 6 hrs 0.64 mL/hr for 18 hrs	12.00	720	06	Start at any convenient time on Day 1; exchange of infusion sets at about 24-hr intervals ¹	As needed	Yes
Regimen 2 ²	60/7.5 mg/mL	5	0.64 mL/hr for 14 hrs	8.96	537.6	67.2	Start in the morning of Day 1; end after 14 hrs or bedtime (whichever occurs first)	Yes: morning dose of LD/CD 150 mg/15 mg and additional LD/DDI as needed	No
Regimen 3 ³			0.75 mL/hr for 16 hrs	12	720	90	Start at any convenient time on Day 1; exchange of infusion sets at 24-hr intervals	Yes: morning dose of LD/DDI and additional LD/DDI as needed ⁴	No

Table 2 Summary of ND0612 SC and oral LD/CD dosing regimens

Pump automatically alternates from low infusion rate to high infusion rate

² Regimen 2 was discontinued on 08 December 2016 and all ongoing subjects who were treated with this regimen were switched to Regimen 1.

³ Introduced with Protocol amendment 2.

⁴ The investigator will determine the dose of daily oral LD/DDI based on the subject's needs.

8.4.8 Blinding

No blinding is foreseen in this open-label study.

8.4.9 Prior and Concomitant Therapy

Any medication taken in addition to the study medication has to be documented in the eCRF with details on the drug, dose, date and reason for prescription.

To be eligible for entering this study, subjects in Cohort 2 have to take at least 4 doses/day of LD (or at least 3 doses/day of Rytary).

Subjects furthermore have to take, or have attempted to take, at least one other PD treatment for at least 30 consecutive days. Subjects must be stable on their anti-PD medications for at least 30 days before Day 1.

Women of childbearing potential who take oral contraception have to continue taking it throughout the whole study.

8.4.9.1 Prohibited Medication/Therapy

If a subject receives prohibited concomitant medication, which cannot be discontinued or reduced, the subject must not enter the trial. If during the study the use of any prohibited medication becomes necessary, the subject will be withdrawn from further participation in the trial. If a subject is withdrawn during the treatment period, the assessments of the Early termination visit have to be performed for this subject.

Subjects may have had prior exposure to SC apomorphine injections/infusion but must have stopped continuous apomorphine infusion administration at least 4 weeks before the screening visit. Treatment with apomorphine is prohibited during the entire ND0612 treatment period. Prior or concomitant neurosurgical procedures for PD or duodopa treatment are also forbidden.

